### 3.2 Secondary Endpoint “c”

#### 3.2.1 Hypotheses

The secondary endpoint “c” is “Successful echoendoscopic fine needle aspiration of PCL, defined as complete cyst aspiration or collection of aspirate adequate to perform two standard assays: cytology and carcinoembryonic antigen (CEA).”

NOTES: Endpoint c) success is defined as:

- complete aspiration, defined as reaching a final cyst maximal diameter of less than 5mm attained with a maximum of 3 needle passes; in the case of a multilocular cyst, complete aspiration of the largest locule is required,

or

- collection of aspirate adequate to perform two standard assays: cytology and CEA, attained with a maximum of 3 needle passes

Total aspirate volume should be 3cc or more. In cases where less than 3cc of aspirate is obtained but cytology and CEA assays can be adequately completed, the secondary endpoint is considered to have been met.

Analysis Approach:

Successful echoendoscopic fine needle aspiration of PCL is calculated overall and for each arm (19 G Flex, 22 G, 19 G).

Hypotheses:

$H_{0i}: \pi_2 - \pi_i \leq 0$  Versus  $H_{1i}: \pi_2 - \pi_i > 0$  for  $i=0, 1$ ;

where  $\pi_0$  is proportion of success in 19 G Arm, and  
 $\pi_1$  is proportion of success in 22 G Arm, and  
 $\pi_2$  is proportion of success in 19 G Flex Arm.

It is the desire of this study to demonstrate superiority of the EUS-FNA 19 G Flex needle over two other needles:

- One offering the same needle diameter, but without added needle flexibility, namely the standard 19 G needle
- One offering better needle flexibility via a reduced needle diameter, namely the standard 22 G needle

Superiority by 16% or more is deemed clinically significant.

The multiple comparison Hochberg's step up method will be used.

The analysis population for the success endpoint will be the Intent to Treat and Per-protocol analysis sets.

### 3.2.2 Sample Size

The sample size was estimated based on the following assumptions:

Design Parameters:

One-sided Type I Error=0.05

Multiple comparison method= Hochberg's step up

Rejection region=Right tail

Treatment Parameters:

Arm	Response rate	Sample size per group
19GFlex	0.91	121
19G	0.75	61
22G	0.75	61

**Overall Power:**Global (reject any  $H_{0i}$ ): 0.947Conjunctive (reject all  $H_{0i}$ ): 0.808

Given the above assumptions, a total sample of 243 subjects will be required where 121 subjects will be in 19 G Flex arm, and 61 subjects in the 19 G and 22 G arms respectively. In order to account for attrition, a total of 250 randomized subjects will be enrolled.

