To create a quantitative hypothesis for the study, a meta-analysis was completed of nine literature reports of EUS-FNA success levels in this indication, using standard, non-flexible EUS-FNA needles. The following references outlined in **Figure 5** were used:

Figure 5 – Hypothesis Generating References (Secondary Endpoint c)

Reference	Success ratio	Success Rate
(1) Brugge	109/112	97.3%
(3) Al-Haddad	31/37	83.8%
(5) Larsen	132/251	52.6%

(6) Khalid	76/113	67.3%
(7) Sawhney	84/100	84.0%
(8) Rogart	75/107	70.1%
(9) Hong	60/69	87.0%
(10) de Jong	80/128	62.5%
(11) Repak	38/38	100%

This yields a success rate point estimate of 75% with 95% CI [67% - 90%] (see **Appendix C.1** for details).

The assumption was made that the success level of both “control groups”, namely the 22 G arm and the 19 G Arm, will be 75%.

Two null hypotheses are made:

- H_{01} : Success rate of 19 G Flex Arm and 22 G Arm are the same
- H_{02} : Success rate of 19 G Flex Arm and 19 G Arm are the same

The alternative hypothesis is:

- H_1 : Success rate of 19 G Flex Arm is superior to both 22 G Arm and 19 G Arm

If 121 patients are enrolled in the 19 G Flex Arm and 61 patients each in the 19 G and 22 G Arm, the study will have 80% conjunctive power to detect the rejection of both null hypotheses to demonstrate superiority of the success rate of 19 G Flex Arm to that of both other arms by 16% or more. Thus, a minimum of 243 patients (121+61+61=243) are required.

Details of the sample size calculation are provided in **Appendix C.2**.

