12 AUG 2016

FINAL

Boston Scientific

Randomized Evaluation of PCLs Using Three EUS-FNA Needles

90869947 Rev/Ver. AG

Page 41 of 46

Design Parameters:

One-sided Type I Error=0.05

Multiple comparison procedure= Hochberg's step up

Total Sample required=100

Rejection region=Right tail

Treatment parameters:

Arm	Mean volume ratio	Standard Deviation	Sample size per group
22G	67	15.29	25
19G	77	4.67	25
19GFlex	77	4.67	50

Overall:

Global (reject any H_i): 0.912

Conjunctive (reject all H_i): 0.901

Secondary endpoint c) considerations:

It is the desire of this study to demonstrate superiority of the EUS-FNA 19 G Flex needle over two other needles:

- One offering the same needle diameter, but without added needle flexibility, namely the standard 19 G needle
- One offering better needle flexibility via a reduced needle diameter, namely the standard 22 G needle

Superiority by 16% or more is deemed clinically significant. Statistical power of 80% is chosen using the multiple comparison Hochberg's method. Test results are shown below, resulting in the requirement for 121 patients for 19 G Flex arm and 61 patients each for 19 G and 22G arm.

Hypothesis:

$H_i: \pi_i - \pi_0 \leq 0$ Versus $K_i: \pi_i - \pi_0 >$ for $i=1,2$

Design Parameters:

One-sided Type I Error=0.05

Multiple comparison procedure= Hochberg's step up

Total Sample required=243

Rejection region=Right tail

Treatment Parameters:

Arm	Response rate	Sample size per group
19GFlex	0.91	121
19G	0.75	61
22G	0.75	61

Overall:

Global (reject any H_i): 0.947

Conjunctive (reject all H_i): 0.808

C.3 Diagnostic Accuracy Measures

Diagnostic accuracy is defined in terms of “disease state” and the following three disease state categories will be used in this study in order to assess diagnostic accuracy of EUS-FNA:

- “*Disease State per EUS-FNA*”: This measure is derived from the results of the cytology and chemistry assays of the cyst aspirate. Cysts will be classified as *serous cyst*, *mucinous cyst*, *IPMN*, or *pseudocyst* based on the table below.⁴ If any of the aspirate assays are not performed or the results from the two aspirate-based assays do not follow the table below, then the Disease State per EUS-FNA will be classified as *Indeterminate*. The Disease State per EUS-FNA will be recorded on the *Cytology and Chemistry Results CRF*.

Disease State per EUS-FNA	Cytology	Cyst Fluid CEA (ng/mL)
Serous	Bland PAS +*	< 0.5
Mucinous	Mucinous	> 200
IPMN	Mucinous	> 200

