### 3 ENDPOINT ANALYSIS

#### 3.1 Primary Endpoint

##### 3.1.1 Hypotheses

The primary endpoint is “Volume of aspirated cyst fluid as a function of estimated maximal volume based on pre-aspiration EUS measure of cyst diameter (s) (% aspiration of total estimated volume).”

Analysis Approach:

% aspiration of total estimated volume is calculated overall and for each arm (19 G Flex, 22 G, 19 G) and/or a combination of arms such as 19G Flex and 19G, for each and combined morphologic characteristics, and for no salvage subjects. If there is multilocular morphology, the primary endpoint is calculated for measurements of the largest locule.

Valid Data Sources:

- Procedure Form: sections “PCL Characteristics” and “Post-Aspiration Assessment”

Valid Data Points:

- Morphology: Unilocular (Pre-aspiration EUS measures)
  - Maximal diameter (long axis) (mm)
  - Perpendicular measurement (short axis) (mm)
- Morphology: Multilocular (Pre-aspiration EUS measures)
  - Measurements of the largest locule
    - Maximal diameter (long axis) of the largest locule (mm)
    - Perpendicular measurement (short axis) of largest locule (mm)
- Total volume of aspirate (Post-aspiration assessment)

Formula:

$$\% \text{ aspiration of total estimated volume} = \frac{A-B}{A} \times 100 \%$$

Volume is computed using the standard geometric formula  $\left(\frac{4}{3}\pi R^3\right)$  where R is half the long axis. The volume unit is in cc. “A” is calculated by the image during pre-procedure measurements. “B” is calculated by the image during post-procedure measurements.

Hypotheses:

$H_{0i}: \mu_i - \mu_0 \leq 0$  Versus  $H_{1i}: \mu_i - \mu_0 > 0$  for  $i=1, 2$ ;

where  $\mu_0$  is mean volume percentage of 22 G Arm,  
 $\mu_1$  is mean volume percentage of 19 G Flex Arm, and  
 $\mu_2$  is mean volume percentage of 19 G Arm.

Superiority by 10% or more is deemed clinically significant.

The multiple comparison Hochberg's step up method will be used.

The analysis population for the primary endpoint will be the Intent to Treat and Per-protocol analysis sets.

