### 3.1.3 Statistical Methods

Two-sample  $t$ -test statistic will be computed as follows.

$$T_i = \frac{\bar{x}_i - \bar{x}_0}{s_{\bar{x}_i - \bar{x}_0}}, \text{ for } i=1, 2;$$

where  $\bar{x}_0$  is mean volume percentage of 22 G Arm,

$\bar{x}_1$  is mean volume percentage of 19 G Flex Arm,

$\bar{x}_2$  is mean volume percentage of 19 G Arm,

$$s_{\bar{x}_i - \bar{x}_0} = \sqrt{\frac{s_i^2}{n_i} + \frac{s_0^2}{n_0}},$$

$n_0$  is sample size of 22 G Arm,

$n_1$  is sample size of 19 G Flex Arm,

$n_2$  is sample size of 19 G Arm.

Now, for each null hypothesis p-value will be computed using one-sided right tail test with type-1 error=0.05 using the following:

$$p_i = P(T_i > t_i) = 1 - \Phi(t_i)$$

where  $T_i$  follows standard normal distribution and  $\Phi(\cdot)$  is cumulative distribution function.

Next, let  $p_{(1)} < p_{(2)}$  be the ordered p-values and  $H_{(1)}, H_{(2)}$  be the associated null hypotheses. The Hochberg step up procedure will be carried out as following:

- Step 1: If  $p_{(2)} > \alpha$  retain  $H_{(2)}$ , otherwise reject all hypotheses and stop.
- Step 2: If  $p_{(1)} > \alpha/(3-1)$  retain  $H_{(1)}$  and stop; otherwise reject  $H_{(1)}$  and stop.

The adjusted p-values for individual hypotheses will be computed by:

$$\tilde{p}_i = \begin{cases} p_{(i)} & \text{if } i = 2 \\ \min(\tilde{p}_{(i+1)}, 2p_{(i)}) & \text{for } i = 1 \end{cases}$$

The adjusted p-value for the global hypothesis will be computed using the following:

$$\tilde{p} = \min(\tilde{p}_1, \tilde{p}_2)$$

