### 3.2.3 Statistical Methods

Test statistics  $T_i$  with pooled variance will be computed as follows.

$$T_i = \frac{\hat{\pi}_2 - \hat{\pi}_i}{\sqrt{\hat{\pi}_i(1 - \hat{\pi}_i)\left(\frac{1}{n_i} + \frac{1}{n_2}\right)}}, \quad i = 0, 1$$

where  $\hat{\pi}_2$  is the sample proportion for 19G Flex arm,

$\hat{\pi}_i$  are the sample proportions for 19G arm and for 22G arm, and

$$\hat{\pi}_i = \frac{n_2 \hat{\pi}_2 + n_i \hat{\pi}_i}{n_2 + n_i}.$$

Now, for each null hypothesis p-value will be computed using one-sided right tail test with type-1 error=0.05 using the following:

$$p_i = P(T_i > t_i) = 1 - \Phi(t_i)$$

where  $T_i$  follows standard normal distribution and  $\Phi(\cdot)$  is cumulative distribution function.

Next let  $p_{(1)} < p_{(2)}$  be the ordered p-values and  $H_{(1)}, H_{(2)}$  be the associated null hypotheses. The Hochberg step up procedure will be carried out as following:

- Step 1: If  $p_{(2)} > \alpha$  retain  $H_{(2)}$ , otherwise reject all the null hypotheses and stop.

- Step 2: If  $p_{(1)} > \alpha / (3 - 1)$  retain  $H_{(1)}$  and stop; otherwise reject  $H_{(1)}$  and stop.

The adjusted p-values for individual hypotheses will be computed by:

$$\tilde{p}_i = \begin{cases} p_{(i)} & \text{if } i = 2 \\ \min(\tilde{p}_{(i+1)}, 2p_{(i)}) & \text{for } i = 1 \end{cases}$$

The adjusted p-value for the global hypothesis will be computed using the following:

$$\tilde{p} = \min(\tilde{p}_1, \tilde{p}_2)$$

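### Endpoint c must show 19 G Flex superior to both standard needles, but its only overall p-value tests superiority to at least one, and its place after the primary is not stated

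*SAP*

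**What the plan says.** Both the primary endpoint (percentage of cyst volume aspirated) and secondary endpoint c have formal hypotheses, a test procedure and a power statement. All other secondary endpoints are only summarised (SAP 5.1.1).

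- **Error level.** SAP 3.1.2 and SAP 3.2.2 each give "One-sided Type I Error=0.05".
- **Multiplicity.** SAP 3.1.1 says "The multiple comparison Hochberg's step up method will be used", and SAP 3.2.1 repeats this for c. Each Hochberg procedure covers only the two hypotheses of its own endpoint. Neither document gives a test order, an alpha split or an error rate across the two endpoints.
- **Aim for c.** The alternative in Protocol 9.1.2 is "Success rate of 19 G Flex Arm is superior to both 22 G Arm and 19 G Arm". Protocol section 1 describes the design as conjunctive. Protocol Appendix C.2 reports "Conjunctive (reject all H_i): 0.808" next to "Global (reject any H_i): 0.947".
- **Overall p-value for c.** SAP 3.2.3 gives the Hochberg steps and individual adjusted p-values, then "The adjusted p-value for the global hypothesis will be computed using the following", followed by the minimum of the two. No sentence says which p-value decides success.
- **Reference distribution.** SAP 3.1.3 calls the primary test a two-sample t-test with unequal variances, but then says that the statistic "follows standard normal distribution and" takes its p-value from the normal distribution function.

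**The concern.** Endpoint c carries the hypothesis of the introduction and sets the trial's size: it needs 243 patients, against 100 for the primary. A reader will treat a significant result on c as a formal finding. Two gaps leave it open what such a result would mean.

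First, the minimum adjusted p-value answers whether Flex beats at least one needle. If it were reported as the result for c, a trial in which Flex only matches standard 19 G could appear to support the intended claim.

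Second, each endpoint has its own full 5%, and nothing says what happens to c if the primary misses. A claim on c after a failed primary would use a second 5%.

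**Working it through.** **Inputs.** For c: success rates 0.91 (Flex) and 0.75 (19 G and 22 G), arms of 121/61/61, one-sided 0.05, pooled-variance z-test with Hochberg (SAP 3.2.2, 3.2.3). For the primary: means 77/77/67, SDs 4.67/4.67/15.29, arms of 50/25/25 for Flex/19 G/22 G (SAP 3.1.2). The correlation between the endpoints within a patient is not given, so r from 0 to 0.9 is assumed.

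**1. Reproducing the plan's power for c.** Exact enumeration gives 0.804 for rejecting both and 0.946 for rejecting any, against the stated 0.808 and 0.947. At one-sided 0.025 the figures are 0.684 and 0.900, so the plan did use the full 0.05.

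**2. 'Any' against 'both' for c.** With two hypotheses, Hochberg rejects both when max(p1, p2) ≤ 0.05. It rejects at least one when that holds or when min(p1, p2) ≤ 0.025. The minimum adjusted p-value is ≤ 0.05 in exactly the second, wider set of cases.

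Suppose Flex = 19 G = 0.91 and 22 G = 0.75. A hand approximation for Flex against 22 G:

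- pooled rate = (121×0.91 + 61×0.75)/182 = 0.856
- pooled SE = √[0.856×0.144×(1/121 + 1/61)] = 0.0551
- unpooled SE = √[0.91×0.09/121 + 0.75×0.25/61] = 0.0612
- power at 0.025 = Φ[(0.16 − 1.96×0.0551)/0.0612] = Φ(0.85) ≈ 0.80

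Exact enumeration of the full rule:

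| True success (Flex, 19 G, 22 G) | min adjusted p ≤ 0.05 | both nulls rejected |
|---|---|---|
| 0.91, 0.91, 0.75 | 81% | 5.5% |
| 0.75, 0.75, 0.60 | 56% | 4.8% |

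**3. Error across the two endpoints.** Two independent tests at 5% give 1 − 0.95² = 9.75%. Simulating all four test statistics with the Hochberg rules gives the chance of at least one false rejection:

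| Situation | No order between endpoints | c formal only after both primary rejections |
|---|---|---|
| No needle differences, r = 0 | 9.3% | 4.7% |
| No needle differences, r = 0.5 | 8.9% | 4.7% |
| No needle differences, r = 0.9 | 7.8% | 4.7% |
| One true null per endpoint, r = 0 to 0.9 | 9.3–10.0% | 5.0% |

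The order columns take c as needing both rejections. The unordered column counts any individual false rejection. Requiring both rejections for c, without an order, lowers the no-difference figure to 5.4% at r = 0 but leaves the one-true-null row at 9.3–10.0%. An order that needs only one primary rejection also leaves that row unchanged.

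**4. Cost of the order.** Primary power to reject both nulls at 121/61/61, for a 10-point effect:

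| SDs | Power |
|---|---|
| Plan (15.29 for 22 G; 4.67 for the others) | 99.9% |
| 15.29 in all arms (assumed) | 97% |
| 20 in all arms (assumed) | 84% |
| 25 in all arms (assumed) | 64% |
| 30 in all arms (assumed) | 48% |

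The range matters because Protocol 9.1.1 derives the SDs by bootstrapping six investigators' estimates of mean volume ratio. These are not shown to be SDs between patients.

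**5. Reference distribution.** At 50/25/25 the normal reference gives power of about 0.913 (both) and 0.926 (any). The t distribution with Satterthwaite degrees of freedom gives 0.904 and 0.915, closer to the stated "Conjunctive (reject all H_i): 0.901" and its global 0.912. With the plan's SDs, the normal reference gives a per-comparison size of 5.2–5.3% at 61 against 121 and at 61 against 61.

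**The case against.** The strongest reply is that the SAP already contains the right decision. Hochberg step 1 rejects both nulls exactly when the larger p-value is at most 0.05, individual adjusted p-values are reported, and the stated 0.808 is power for both. The minimum is labelled as the p-value for the global hypothesis and matches the global power line. No sentence makes it the success criterion. All of this stands. What remains is that no sentence names the criterion, and the one overall p-value supplied is the wrong one for the stated alternative.

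Three stronger readings are tempting, and the documents do not support them.

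- A reader might infer that the trial's false-claim rate is 9–10%. Endpoint c is labelled secondary, neither document promises 5% across both endpoints, and the primary family alone stays near or below 5%. The higher figure needs c to be claimed whatever the primary shows, on which the documents are silent.
- A reader might take the 81% as an error rate. In that scenario Flex really is better than 22 G, so the global null is false and 81% is power.
- A reader might blame the minimum p-value for the 8–10%. The two issues are separate: with one true null per endpoint, 9.3–10.0% remains even when c needs both rejections.

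A fair objection to the remedy is that a fixed order is one valid choice among several, and that it makes a Flex claim on c wait for standard 19 G to beat 22 G on volume. That also stands and is part of the cost.

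**Conclusion.** The point holds as two limited gaps and one minor inconsistency.

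- The success criterion for c is not stated, and the only overall p-value does not match the alternative. If that p-value were used for the claim of superiority to both, it would be significant in 56–81% of trials in the two scenarios where Flex merely equals 19 G, against about 5% for the correct rule.
- With no order between the endpoints, the chance of at least one false claim is about 8–10%, conditional on c being claimed regardless of the primary. The lower end applies when there are no needle differences and the endpoints are strongly correlated. Positive correlation is likely, because the volume formula in SAP 3.1.1 and complete aspiration in SAP 3.2.1 both use the post-procedure diameter.
- The normal reference in SAP 3.1.3 has little effect on size, but it is inconsistent with the named test and fits the stated power less well.

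The success rates are the plan's own or illustrative. The correlations and the equal SDs are assumptions.

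**What to change.** 1. **SAP 3.2.3.** State that c succeeds only if both nulls are rejected, that is max(p1, p2) ≤ 0.05 (Hochberg step 1). This matches the conjunctive power of 0.808 used for sizing. Do not use the global minimum p-value as the success criterion. This costs only wording.
2. **SAP 3.2.** State that c is a formal claim only after the primary family succeeds and is otherwise descriptive. Define primary success as rejection of both primary nulls, since a single rejection does not hold the error near 5%. The cost is that c, the endpoint that sized the trial, can be lost if the primary misses. Disclose the range of primary power: 99.9% under the plan's SDs, and 97%, 84%, 64% and 48% with equal SDs of 15.29, 20, 25 and 30. The alternative of 0.025 per endpoint avoids this dependence but lowers power for c to reject both from 0.804 to 0.684.
3. **SAP 3.1.3.** Take p-values from the t distribution with Satterthwaite degrees of freedom. The power loss at the planned arm sizes is negligible.

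All three are SAP text changes, to be made before the final analysis.

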### 3.2.3 Statistical Methods

Test statistics  $T_i$  with pooled variance will be computed as follows.

$$T_i = \frac{\hat{\pi}_2 - \hat{\pi}_i}{\sqrt{\hat{\pi}_i(1 - \hat{\pi}_i)\left(\frac{1}{n_i} + \frac{1}{n_2}\right)}}, \quad i = 0, 1$$

where  $\hat{\pi}_2$  is the sample proportion for 19G Flex arm,

$\hat{\pi}_i$  are the sample proportions for 19G arm and for 22G arm, and

$$\hat{\pi}_i = \frac{n_2 \hat{\pi}_2 + n_i \hat{\pi}_i}{n_2 + n_i}.$$

Now, for each null hypothesis p-value will be computed using one-sided right tail test with type-1 error=0.05 using the following:

$$p_i = P(T_i > t_i) = 1 - \Phi(t_i)$$

where  $T_i$  follows standard normal distribution and  $\Phi(\cdot)$  is cumulative distribution function.

Next let  $p_{(1)} < p_{(2)}$  be the ordered p-values and  $H_{(1)}, H_{(2)}$  be the associated null hypotheses. The Hochberg step up procedure will be carried out as following:

- Step 1: If  $p_{(2)} > \alpha$  retain  $H_{(2)}$ , otherwise reject all the null hypotheses and stop.

- Step 2: If  $p_{(1)} > \alpha / (3 - 1)$  retain  $H_{(1)}$  and stop; otherwise reject  $H_{(1)}$  and stop.

The adjusted p-values for individual hypotheses will be computed by:

$$\tilde{p}_i = \begin{cases} p_{(i)} & \text{if } i = 2 \\ \min(\tilde{p}_{(i+1)}, 2p_{(i)}) & \text{for } i = 1 \end{cases}$$

The adjusted p-value for the global hypothesis will be computed using the following:

$$\tilde{p} = \min(\tilde{p}_1, \tilde{p}_2)$$

## 4 GENERAL STATISTICAL METHODS

### 4.1 Analysis Sets

The Intent-to-treat (ITT) cohort will consist of all randomized subjects, namely subjects who signed the ICF, met all eligibility criteria (see note below), were randomized to one of three study arms, and experienced echoendoscope insertion and attempted EUS-FNA procedure. Subjects in this cohort, independent of whether or not the EUS-FNA was successful, will be counted towards the enrollment ceiling. Any adverse events occurring or resulting from a treatment attempt will be collected.

NOTE:

Exclusion criteria #1 may be documented after a subject was randomized and the EUS procedure was started. In such cases, the subject will be excluded from the study and no longer be a part of the ITT cohort.

The Modified Intent-to-treat population will consist of ITT population with salvage, namely the subjects with 19G + Salvage, 22G + Salvage, and 19G Flex+ Salvage.

The per-protocol (PP) cohort will consist of the subset of the ITT subjects in whom the target lesion could be reached and EUS-FNA yielded any aspirate, used the assigned needle, and there were no major protocol deviations.

All endpoints will be analyzed for all subjects and stratified by EUS-FNA needle type (by randomization arm) for the ITT analysis set. Similarly, primary and selected secondary endpoints will be analyzed for the PP analysis set.

### 4.2 Demographics, Baseline Characteristics and Medical History

Subject demographic information will be summarized. The demographic summary includes subjects' gender and age. The baseline characteristics include: medical history, diabetes, chronic pancreatitis, and necrotizing pancreatitis.

